# Guidelines for close observation for potential drug induced liver injury:

Within 72 hours, perform a symptom directed history, physical, and liver biochemistries, including evaluation of:

- New or worsening signs and symptoms of clinical hepatitis such as fatigue, nausea, vomiting, right upper quadrant pain or tenderness, fever, rash, or eosinophilia
- Concomitant medications, including acetaminophen, dietary supplements, herbal remedies, over-the-counter medications, recreational drug use, and special diets
- Alcohol consumption
- Exposure to environmental chemical agents
- Past medical history
- Complete review of systems
- Liver biochemistries including ALT, AST, alkaline phosphatase, total bilirubin, and INR

Evaluate patients for signs and symptoms of clinical hepatitis and obtain liver biochemistries until biochemistries stabilize.

If biochemistries stabilize and the subject is asymptomatic, monitor liver biochemistries once a week until they return to baseline.

Subjects who live far from study sites may be evaluated locally for history, physical exam, and laboratories, if the results are communicated promptly to the site investigator.

# 16.2 Local Injection Site Reactions (LISRs)

The following MedDRA Preferred Terms determined by the Sponsor's pharmacovigilance personnel represent the local injection site reaction:

Injection site discomfort	Injection site abscess
Injection site discoloration	Injection site abscess sterile

Injection site erythema	Injection site atrophy
Injection site irritation	Injection site calcification
Injection site inflammation	Injection site cellulitis
Injection site induration	Injection site dermatitis
Injection site pain	Injection site erosion
Injection site oedema	Injection site fibrosis
Injection site pruritus	Injection site indentation
Injection site rash	Injection site necrosis
Injection site urticaria	Injection site nodule
Injection site reaction	Injection site ulcer
Injection site swelling	

LISRs will only include events that start on the day of injection and persist for at least 48 hours post injection (i.e., event onset date on the day of injection and resolution date not on the day of injection or the day after the injection) will be included. Events with onset date on the day of injection and missing resolution date will also be included in the summary.

The following calculation will be utilized to determine the percentage of injections leading to local injection site reactions:

 $(A/B)^*$ , where A = number of injections with a local injection site reactions, and B = total number of injections.

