#### 11.4 Recording of AEs

When an AE occurs, it is the responsibility of the PI or medically qualified designee to review all documentation (e.g., hospital progress notes, laboratory, and diagnostics reports) relative to the event. The PI or medically qualified designee will then record the AE on the AE CRF. Additional reporting requirements for an AE that meets serious criteria are discussed in Section 11.7 below.

The PI or medically qualified designee will attempt to establish a diagnosis of the event based on signs, symptoms, and/or other clinical information. In all cases, when available, the diagnosis should be reported as the event and not the individual signs/symptoms. It is not acceptable for the PI to send photocopies of the patient's medical records to the Sponsor in lieu of completion of the appropriate AE eCRF pages.

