# 11.5.2 AEs at the Injection Site and Local Injection Site Reactions (LISRs)

AEs at the injection site will be graded as either Mild, Moderate or Severe. A local injection site reaction is defined as an adverse reaction (usually immunologic) developing at the site of injection and lasting at least 48 hours. For the data reporting and analysis purposes, the definition of LISR based on duration of at least 48 hours and based on the specified MedDRA preferred times is provided in Appendix 16.2. Photographs of local reactions around injection site should be obtained at the time of reporting and at the approximate time of resolution.

- Mild: Tenderness with or without associated symptoms (e.g., warmth, erythema, itching), mild pain or mild edema
- Moderate: Pain with associated phlebitis or lipodystrophy
- Severe: Tissue ulceration or necrosis with associated severe tissue damage or if operative intervention is indicated

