5. DEFINITIONS

Day 1:

For each subject, Day 1 is defined as the first day that protocol-specified study treatment is administered to the subject.

End of Study (EOS) Date:

For each subject, the EOS date is the study completion/early termination date recorded on the eCRF.

Study Day:

For each subject, and for a given date of interest, study day is defined as the number of days relative to Day 1:

- After first dose date: study day = date of interest – Day 1 date + 1
- Prior to first dose date: study day = date of interest – Day 1 date, so that the day prior to Day 1 is Day -1

Study End Date:

The study end date is when the last subject finishes the EOS visit.

Baseline Values:

For all variables, baseline is defined as the last non-missing value obtained prior to the first dose administration on Day 1.

For ECG, if a triplicate is taken prior to the first dose administered on Day 1, baseline is defined as the mean over the set of triplicate assessments.

Analysis Day:

Selected endpoints will be summarized based on Analysis Day defined using Study Day as below.

Scheduled Visit/ Analysis Day	Day 8	Day 15	Day 29	Day 43	Day 57	Day 71	Day 85	Day 99	Day 113
Study Day Window Cohort 1-4	[6,10]	[13,17]	[27,31]	[41, 45]	[55,59]	[69,73]	[83,87]	[97,101]	[111,115]
Study Day Window Cohort 1b,3b,4b	NA	[13,17]	[27,31]	NA	[55,59]	[66,76]	[83,87]	NA	[108,118]

If there is more than one record in a study day window, the analytical record for that specific analysis day will be defined as the record closest to the scheduled visit day. If two records are equidistant from the scheduled visit day, then the earlier record will be chosen. If there are multiple records on the same day, the last record will be used.

Duration of study:

EOS date – Day 1 date + 1

Treatment-Emergent Adverse Event (TEAE):

TEAEs are defined as adverse events occurring on or after the first dose of study treatment through EOS or pre-treatment existing conditions that worsen after the investigational product administration.

Treatment-emergent SAEs (TESAEs):

TESAEs are defined as serious adverse events occurring on or after the first dose of study treatment through EOS or pre-treatment existing conditions that worsen after the investigational product administration.

TEAE at Injection Site:

TEAE occur at the injection site. MedDRA Preferred Terms which are included in LISR are listed in Protocol Section 16.2.

TEAE Related to Local Injection Site Reaction (LISR):

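### The term list that defines an LISR names neither phlebitis nor lipodystrophy, the features that make a reaction Moderate, so a reaction recorded under either diagnosis can drop out of the LISR summaries

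*Protocol*

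**What the plan says.** Appendix 16.2 of the protocol introduces its list with the words "The following MedDRA Preferred Terms determined by the Sponsor's pharmacovigilance personnel represent the local injection site reaction". It then gives 25 terms, all of the form Injection site plus a finding, with no examples clause and no catch-all. Section 11.5.2 makes this list, together with a minimum duration of 48 hours, the definition for reporting and analysis: "based on the specified MedDRA preferred times is provided in Appendix 16.2" (times is evidently a slip for terms).

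Section 11.5.2 grades injection-site events in three steps. The middle step reads "Moderate: Pain with associated phlebitis or lipodystrophy". The step below it, Mild, rests on tenderness, slight pain or slight swelling, and gives warmth, redness and itch as possible accompanying signs. The step above it, Severe, needs ulcerated or necrotic tissue with serious damage, or a need for surgery.

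On what the site should enter, section 11.4 says: "In all cases, when available, the diagnosis should be reported as the event and not the individual signs/symptoms".

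SAP section 5 adds no terms. Under both TEAE at Injection Site and TEAE Related to LISR it states: "MedDRA Preferred Terms which are included in LISR are listed in Protocol Section 16.2". SAP section 9.6.1 plans tables for each of these two categories, including tables by severity. Appendix 16.2 also defines a percentage of injections with an LISR, A/B.

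**The concern.** The grading scale and the term list serve the same output, the summary of LISRs by severity, but they do not match at the Moderate step. Within 11.5.2 the only route to Moderate is pain accompanied by phlebitis or lipodystrophy, and neither has a listed term. A site that follows 11.4 and enters the diagnosis may thus produce a record that satisfies the Moderate grade, the onset rule and the duration rule, and still fails the term filter.

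What is at stake is the study's specific summary of local tolerability. Section 5.7 names injection site reactions as a risk, describes those seen with similar drugs as mild to moderate, and relies on grading by predefined criteria. The Moderate grade is therefore within the range that the protocol expects to see.

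**Working it through.** The plan states no figure to reproduce here. The check compares two lists and then works out the weight of one event.

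**Step 1. Grading features in 11.5.2 against the 25 terms in 16.2.**

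| Feature | Grade | Listed term |
|---|---|---|
| Tenderness | Mild | none by name; pain and discomfort are the closest |
| Warmth | Mild (accompanying symptom) | none |
| Erythema | Mild | erythema |
| Itching | Mild (accompanying symptom) | pruritus |
| Pain | Mild; head term of Moderate | pain |
| Edema | Mild | oedema |
| Phlebitis | Moderate | none |
| Lipodystrophy | Moderate | none by name; atrophy and indentation may catch some forms |
| Ulceration | Severe | ulcer |
| Necrosis | Severe | necrosis |

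Both features that separate Moderate from Mild are unmatched by name. Both tissue features of Severe are matched.

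**Step 2. One Moderate reaction, several possible records.** Take pain with phlebitis or lipodystrophy that starts on the injection day and lasts 3 days. Under 16.2:

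- recorded as injection site pain: counted;
- recorded as injection site inflammation or injection site reaction: counted;
- lipodystrophy recorded as injection site atrophy or indentation: counted;
- recorded as phlebitis or as lipodystrophy: not counted.

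If onset falls after the injection day, 16.2 excludes the event whatever its term. SAP section 5 words the onset rule differently, placing it on the day after the injection. That inconsistency is separate and needs its own reconciliation; the gap in the list is the same under either wording.

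**Step 3. Weight of one missed event.** Inputs are the Cohort Summary (Table 4) and section 10.5, under which each dose is one injection.

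- Healthy volunteers: 4 cohorts × 8 = 32 injections, 16 active and 16 placebo.
- Patients: 3 cohorts × 6 patients × 2 doses = 36 injections, all active.
- Total: 32 + 36 = 68 injections, of which 16 + 36 = 52 are active.

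Each otherwise missed injection would raise A by 1, so the change in A/B is 100/B points:

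| Denominator B | Change for one event |
|---|---|
| 4 (active group of one volunteer cohort) | 25 points |
| 12 (full patient cohort) | 8.33 points |
| 52 (all active injections) | 1.92 points |
| 68 (all injections) | 1.47 points |

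Counted by subject, one missed subject is 1/4 = 25 points in a volunteer active group and 1/6 = 16.7 points in a patient cohort of six.

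**The case against.** The strongest case on the other side is that little is actually lost.

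- **Pain is the head term of the Moderate grade and is listed.** Section 11.4 applies only when a diagnosis is available and does not say which diagnosis to choose. A reader might infer that every Moderate reaction falls out of the table. The documents do not support that: Step 2 shows several ordinary recordings that are counted. This stands, and it limits the point to records made under the two missing names.
- **The list is not weighted towards Mild signs.** It contains ulcer, necrosis, abscess, cellulitis, erosion, fibrosis and calcification. A reader might infer a general bias towards few and mild reactions. That does not follow; the gap is at one step of the scale.
- **Warmth is a weak example.** Section 11.5.2 names it only as a symptom accompanying tenderness, so it matters only if recorded alone. It belongs in the fix for completeness and carries no weight in the argument.
- **The onset rule already removes late events.** Lipodystrophy that appears after the injection day would fail 16.2 with or without a matching term. This stands; added terms help only events that also meet the onset rule.
- **The broader SAP category may be unrestricted.** A reader might infer that the TEAE at Injection Site table loses the same events. SAP section 5 first describes that category simply by location, and the reference to 16.2 can be read as information about LISRs. Section 9.6.1 tabulates the two categories separately, which fits a broader first one. The wording is ambiguous, and no more than that can be claimed.
- **No safety data disappear.** Treatment-emergent events remain in the overall tables by system organ class and preferred term, by severity and by relationship, and in the listings. The primary endpoint, related adverse events, is unaffected.

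What survives is the mismatch itself. A closed analysis definition omits the two diagnoses on which the protocol's own grading scale turns, and the recording rule makes it plausible that those diagnoses will be entered.

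**Conclusion.** The concern holds in a limited form. A reaction that meets the onset and duration rules in 16.2 and is recorded as phlebitis or lipodystrophy can be left out of the LISR-by-severity table and of the A/B percentage. The same reaction recorded as injection site pain, inflammation, reaction, atrophy or indentation is counted.

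The total effect cannot be sized, because the documents give no frequency for such events. One event is worth 8.3 points in a full patient cohort and 1.9 points over all planned active injections. These figures assume six patients per cohort, both doses given, and one injection per dose. How the coding dictionary would treat a particular verbatim term is not in the documents and is not relied on.

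This is a minor point about a descriptive safety table. It is worth correcting because a stated analysis rule conflicts with the protocol's own grading scale and the correction is small.

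**What to change.** 1. In Appendix 16.2, add the injection-site preferred terms for phlebitis and lipodystrophy and, for completeness, warmth. The exact term names should be taken from the MedDRA version used for coding. The list then matches the distinguishing features in 11.5.2.
2. In SAP section 5, state that TEAE at Injection Site covers all treatment-emergent events coded to any injection-site preferred term and is not restricted to the LISR list.

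The cost is a few added terms and one SAP sentence, with no new data collection. The only downside is that the reported LISR count may rise slightly.

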9.6.1 Adverse Events

Adverse event (AEs) will be coded using the Medical Dictionary for Regulatory Activities (MedDRA, the latest available version) and data will be summarized by System Organ Class (SOC) and a Preferred Term.

A table providing an overall summary of AEs will be produced which will include the number of TEAEs; the number and percentage of participants reporting at least one: TEAE, TESAE, grade 3 (severe) or higher TEAE, TEAE related to study treatment (possibly or probably related to ARO-HSD), TESAE related to study treatment, grade 3 or higher TEAE related to the investigational product and TEAE leading to drug or study withdrawal.

Descriptive statistics summaries of subject incidence will be summarized for all TEAEs, treatment-related TEAEs, TESAEs, treatment-related TESAEs, and TEAEs resulting in investigational product withdrawal or study discontinuation, treatment emergent fatal AEs, TEAE at injection site and TEAE related to LISR will be tabulated by SOC in alphabetical order and PT in descending order of frequency. Descriptive summaries will include count and percent of subjects as well as number of events..

Descriptive statistics summaries of subject incidence of TEAEs, TEAE at injection site and TEAE related to LISR by SOC, PT, and severity will be provided. Subjects will be counted once under the highest severity reported within each SOC and PT. The events will be counted the number of times they occur within each SOC and PT.

Descriptive statistics summaries of subject incidence of TEAEs by SOC, PT, and relationship to investigational product will be provided. Subjects will be counted once under the closest relationship reported within each SOC and PT. Events will be counted the number of times they occur within each SOC and PT.

A by-subject AE data listing, including verbatim term, MedDRA SOC and PT, TEAE flag, seriousness, severity, outcome and relationship to study treatment will be provided. Separate listings will be generated for SAEs.

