The number of subjects receiving study treatment will be summarized by the total number of injections received and the duration of study. Duration of study will be calculated in weeks as: (EOS date – date of first dose + 1)/7.

9.6.9 *Exposure to Concomitant Medication*

Medications with an end date on or after the first dose of investigational product will be identified as concomitant medications. Medications will be coded using World Health Organization Drug Dictionary (WHO-DD, the latest available version). and will be reported by Anatomical Therapeutic Chemical (ATC) classification level 4 and Preferred Drug Name.

Participants who take the same medication more than once will be counted only once for that preferred term.

Descriptive statistics summaries of the number and percent of subjects who receive each concomitant medication will be summarized.

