10. CHANGES FROM PROTOCOL-SPECIFIED ANALYSES

As of this date, there have been no changes between the protocol-defined statistical analyses and those presented in this statistical plan.

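### The protocol commits to reporting the percentage of injections with a local injection site reaction; the SAP omits it, declares no changes, and its planned tables cannot supply the figure for the two-injection patient cohorts

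*Protocol*

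**What the plan says.** Protocol 16.2 lists the qualifying preferred terms, sets an onset and duration rule, and then commits to a calculation: "The following calculation will be utilized to determine the percentage of injections leading to local injection site reactions", "where A = number of injections with a local injection site reactions, and B = total number of injections". Protocol 11.5.2 sends the reader to that appendix for the LISR definition used in reporting and analysis.

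SAP 9.6.1 plans LISR tables in a different unit: "TEAE at injection site and TEAE related to LISR will be tabulated by SOC in alphabetical order and PT in descending order of frequency". Their content is set out next: "Descriptive summaries will include count and percent of subjects as well as number of events". In the severity version, "Subjects will be counted once under the highest severity reported within each SOC and PT", while events are counted each time they occur. The SAP cites Protocol 16.2 only for its list of preferred terms (section 5). Injection counts appear only in the exposure summary, SAP 9.6.8: "The number of subjects receiving study treatment will be summarized by the total number of injections received and the duration of study". They are not linked to reactions.

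SAP section 10 says that "there have been no changes between the protocol-defined statistical analyses and those presented in this statistical plan".

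The two documents also date an LISR differently. Protocol 16.2 requires onset on the day of injection; SAP section 5 puts it on the day after.

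**The concern.** Safety and tolerability are the study objective. Injection site reactions are a named risk in Protocol 5.7, and LISRs are a listed safety assessment in Protocol 10.7. A per-injection rate is the natural summary here because exposure differs by design. Volunteers, including every placebo subject, receive one injection. Patients receive two, at dose levels shared with volunteer cohorts (25 mg, up to 100 mg and up to 200 mg). A percentage of subjects accumulates over injections, whereas a percentage of injections does not.

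Two things are at stake. A calculation that the protocol promised would be missing from the study report without explanation. In addition, a reader who sets the patient tables beside the volunteer or placebo tables could take extra exposure for poorer local tolerability.

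**Working it through.** **Inputs.**
- Subjects (Protocol 7.1 Table 4 and 7.2): 4 volunteer cohorts × 8 = 32, of whom 16 are active and 16 placebo; 3 patient cohorts × 6 = 18, all active. The total of 32 + 18 = 50 reproduces the planned enrolment of about 50.
- Doses per subject (Protocol synopsis): one for volunteers, two for patients, 28 days apart.
- Injections per dose (Protocol 10.5): one.
- Planned injections: 32 × 1 = 32 in volunteers (16 active); 18 × 2 = 36 in patients.
- LISR rate per injection, p: the documents give none, so p is an assumption and is varied.

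**Step 1. Can A/B be recovered from the planned tables?**
- Volunteers: with one injection each, injections with an LISR equal subjects with an LISR. The percentage of subjects with any LISR is therefore A/B, provided that subjects are counted across all preferred terms together.
- Patients: let s of the 6 patients in a cohort have at least one LISR, with both doses given to all. Then A can be anything from s (one reacting injection each) to 2s (both reacting), and B = 12. A/B lies between s/12 and 2s/12, that is, between half the subject percentage and all of it.
- Event counts do not settle A. Protocol 16.2 lists 25 qualifying terms, and SAP 9.6.1 counts events within each term, so an injection followed by pain and erythema can count as two events.

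**Step 2. Subject percentage at an equal per-injection rate.**
- One injection: p.
- Two injections with within-subject correlation ρ: 2p − [p² + ρp(1 − p)].
- Ratio of two injections to one: 2 − p − ρ(1 − p). For ρ between 0 and 1 this runs from 1.0 (ρ = 1) to 2 − p (ρ = 0).

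| Assumed p | One injection | Two, ρ = 0 (ratio) | Two, ρ = 0.5 | Two, ρ = 1 |
|---|---|---|---|---|
| 5% | 5% | 9.75% (1.95) | 7.38% | 5% |
| 10% | 10% | 19% (1.90) | 14.5% | 10% |
| 20% | 20% | 36% (1.80) | 28% | 20% |
| 30% | 30% | 51% (1.70) | 40.5% | 30% |
| 50% | 50% | 75% (1.50) | 62.5% | 50% |

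**Step 3. The same situation on the protocol's measure.** At p = 20%, the expected A/B is 3.2/16 = 20% in active volunteers and 7.2/36 = 20% in patients, whatever the correlation. On subject percentages with independent injections, the same p gives 3.2/16 = 20% and 6.48/18 = 36%.

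**Step 4. Reacting injections per subject.** The expected number is p for volunteers and 2p for patients, a ratio of 2 at any correlation. If every reaction were coded to two terms, expected events per subject would be 2p and 4p, and the ratio would still be 2.

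**The case against.** The strongest reply is that the SAP does what the protocol's own analysis section asks. Protocol 12.3 calls for participants with each preferred term and for event counts, and SAP 9.6.1 delivers these and adds dedicated injection-site and LISR tables. A/B sits in an appendix and is not a listed endpoint. This stands: a reader might infer that the SAP swapped the protocol's measure for another, but the documents show a supplementary calculation left out, not replaced.

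It is also fair that no comparison of volunteers with patients is planned. SAP 9.1 presents the two populations separately and SAP 2.2 tests no formal hypotheses. Within volunteers, and among patients who received both doses, exposure is equal and nothing is distorted. With 4 active volunteers or up to 6 patients per dose, one subject moves a percentage by 25 or about 17 points, so any ratio would be read loosely.

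Independence of a patient's two injections cannot be assumed either. Protocol 11.5.2 describes these reactions as usually immunologic, which makes positive correlation plausible.

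A could be counted by hand from the by-subject listings, because doses are 28 days apart. That shows the table is feasible; it does not put the calculation in the plan. The table shells are in a companion document not available here, so a per-injection table may exist there, but the SAP text does not call for one.

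None of this answers the statement in SAP section 10, which is inaccurate on this point.

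**Conclusion.** The point holds as an undeclared omission. Protocol 16.2 promises A/B, the SAP does not plan it, and for the three patient cohorts the planned tables cannot supply it. This follows from the text and needs no assumption about rates.

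The effect on interpretation is conditional. It arises only if patients are compared with volunteers or pooled placebo, and its size is a factor between 1.0 and just under 2 in the subject percentage, depending on an assumed rate and an unknown, non-negative within-subject correlation. At an assumed 20% rate the factor is 1.8 if injections are independent and 1.4 at correlation 0.5.

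Two stronger readings are tempting and are not supported. One is that patients will look 1.7 to 1.95 times worse. That range needs independent injections, rates of 5% to 30%, and a comparison that the SAP does not plan. The other is that coding one reaction to several terms widens the gap further. It raises event counts in both populations alike and leaves their ratio unchanged, and Protocol 11.4 limits such coding by asking for a diagnosis in place of individual signs where one is available.

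**What to change.** 1. Reconcile the LISR onset rule between Protocol 16.2 (day of injection) and SAP section 5 (day after). Until then the numerator A is not settled.
2. Add to SAP 9.6.1 one table of A/B: injections with at least one LISR over total injections, by dose, separately for volunteer and patient cohorts, with pooled placebo. Count each injection once, whatever the number of preferred terms.
3. Keep the subject and event tables.
4. If the sponsor prefers not to report A/B, state and justify the omission in SAP section 10.

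The cost is one descriptive table and a definition to align. The injections needed for B are already counted for the exposure summary in SAP 9.6.8, and A needs only event dates matched to injection dates. No new data are required.
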